7.5 Dose modifications for adverse events

7.5.1 Dose reduction guidelines

For patients who are unable to tolerate the protocol-specified dosing schedule, dose adjustments are permitted in order to keep the patient on study drugs. If administration of panobinostat, MLN9708 (ixazomib), or dexamethasone must be interrupted because of unacceptable toxicity, drug dosing will be interrupted or modified according to guidelines outlined below. Clinical judgment may be used when deciding which drug to hold or modify in scenarios that are not covered below. Also, if the treating physician feels dose reduction by one level will not suffice to avoid recurrence of an observed profound adverse event, dose reduction by more than one dose level or before the severe adverse event occurs is allowed. If an adverse event is felt not related to study drug but continued use of study drugs may worsen the adverse event, holding the respective study drug until resolution of the adverse event without dose reduction at re-initiation of therapy is allowed. Toxicity will be assessed using the NIH-NCI Common Terminology Criteria for Adverse Events, version 4.03 (CTCAEv4.03, (http://ctep.cancer.gov/protocolDevelopment/electronic_applications/docs/ctcae4.pdf)). All interruption or changes to study drug administration must be recoded.

7.5.2 Dose Re-Escalation Guidelines

If an entire cycle was tolerated without need for dose reduction and it is felt that the patient may tolerate a re-escalation of study therapy due to improved disease control or optimized supportive measures, doses may be increased by one level per cycle for either ixazomib (MLN9708) or panobinostat with or without concurrent increase of dexamethasone up to maximally starting dose level.

Table 7-1 Dose modification (DM) levels for adverse events attributed to MLN9708

DM Level	MLN9708 dose modification dependent on starting dose (maintain schedule of administration on day 1,8,15 every 28 days in all DM levels)	
	Starting dose	
0	3mg	4mg
-1	2.3mg	3mg
-2	Discontinue MLN9708	2.3mg
-3		Discontinue MLN9708

Table 7-2 Dose modification (DM) levels for adverse events attributed to panobinostat

DM Level	Panobinostat dose (maintain schedule of administration on d 1,3,5,15,17,19 q 28 d in all DM levels)
0	20mg
-1	15mg
-2	10mg
-3	5mg
-4	Discontinue panobinostat

Dose modification (DM) levels for adverse events attributed to panobinostat and MLN9708

Modify dosing schedules as outlined in table 7-1 and 7-2 alternating between panobinostat and MLN9708, starting with panobinostat

Table 7-3 Dose modification (DM) levels for adverse events attributed to dexamethasone

DM Level	Dexamethasone
0	20mg d 1,2,8,9,15,16 q 28 d

-1	20mg d 1,8,15,22 q 28 d
-2	16mg d 1,8,15,22 q 28 d
-3	12mg d 1,8,15,22 q 28 d
-4	Discontinue dexamethasone

7.5.3 Dose modifications for study drug-related toxicity (see section 7.5.4 for dose modifications for prolonged QTc):

The criteria for dose modifications for study drug-related toxicity are detailed in table 7-4.

Table 7-4 Criteria for dosing delays, dose-reductions, and re-initiation of treatment due to study drug-related toxicity (excluding QT prolongation)

Worst Toxicity CTCAE Grade* unless otherwise specified (Value)		Dose Modification Guidelines At any time during a cycle of therapy (including intended day of dosing)
HEMATOLOGICAL TOXICITIES		
Thrombocytopenia	Grade 4 (< 25 x 10 ⁹ /L)	Temporarily discontinue panobinostat and MLN9708 dosing until platelets have increased to ≥ 50 x 10 ⁹ /L, then reduce dose of one of these drugs by one level per cycle starting with panobinostat until panobinostat is at 10mg, then alternate with ixazomib dose reductions

Worst Toxicity CTCAE Grade* unless otherwise specified (Value)		Dose Modification Guidelines At any time during a cycle of therapy (including intended day of dosing)
Neutropenia (ANC)	Grade 4 (ANC < 0.5 x 10 ⁹ /L)	Temporarily discontinue panobinostat and MLN9708 dosing and consider use of G-CSF or GM-CSF until the ANC has increased to $\geq 0.5 \times 10^9/L$, then reduce dose of one of these drugs by one level per cycle starting with panobinostat until panobinostat is at 10mg, then alternate with ixazomib dose reductions. If neutropenia was the only reason for dose reduction, consider maintaining the same dose level with prophylactic use of G-CSF or GM-CSF in the next cycle when neutrophil counts decrease below $1 \times 10^9/L$.
	Febrile neutropenia (ANC < 1.0 x 10 ⁹ /L, fever $\geq 38.5^\circ C$)	Temporarily discontinue panobinostat and MLN9708 dosing and consider use of G-CSF or GM-CSF until fever resolved and ANC \leq grade 2, then reduce dose of one of these drugs by one level per cycle starting with panobinostat until panobinostat is at 10mg, then alternate with ixazomib dose reductions.

Worst Toxicity CTCAE Grade* unless otherwise specified (Value)		Dose Modification Guidelines At any time during a cycle of therapy (including intended day of dosing)
NON-HEMATOLOGICAL TOXICITIES		
CARDIAC		
Cardiac - Prolonged QT interval**		Please refer to Section 7.5.4.
PERIPHERAL NEUROPATHY		
Grade 1-2 with clinically significant impact on quality of life		Consider holding ixazomib (MLN9708) and restarting at reduced level upon satisfactory improvement
Grade 3		Hold ixazomib (MLN9708) and restart at reduced level upon resolution to Grade \leq 1 or baseline.
Grade 4		Permanently discontinue ixazomib (MLN9708)
RASH		
Grade 2		Symptomatic recommendations as per section 7.6
GASTROINTESTINAL		
Diarrhea	Grade 2 (4-6 stools/day over baseline, etc.) despite the use of optimal antidiarrheal medications	Temporarily discontinue panobinostat and MLN9708 dosing until resolved to \leq grade 1, or baseline, then restart at unchanged dose levels at the first occurrence. If this adverse event recurs at grade 2 in subsequent cycles reduce dose by one level alternating between panobinostat and MLN9708, starting with panobinostat.
	Grade 3 (\geq 7 stools/day over baseline, etc.) despite the use of optimal antidiarrheal medications	Temporarily discontinue panobinostat and MLN9708 dosing until resolved to \leq grade 1, or baseline, then reduce dose by one level alternating between panobinostat and MLN9708, starting with panobinostat.

Worst Toxicity CTCAE Grade* unless otherwise specified (Value)		Dose Modification Guidelines At any time during a cycle of therapy (including intended day of dosing)
	Grade 4 (life-threatening consequences, hemodynamic collapse, etc.) despite the use of optimal antidiarrheal medications	Take patient off study.
Nausea/vomiting	Grade 1 & 2 not requiring treatment or controlled using standard anti-emetics	Maintain dose levels of panobinostat, MLN9708, and dexamethasone.
	Grade 3 or 4 vomiting or Grade 3 nausea that cannot be controlled despite the use of standard anti-emetics	Temporarily discontinue panobinostat and MLN9708 dosing until resolved to \leq grade 1, or baseline, then reduce dose by one level alternating between panobinostat and MLN9708, starting with panobinostat.
FATIGUE		
Fatigue	Grade 3 (fatigue not relieved by rest limiting self-care activities of daily life)	Temporarily discontinue panobinostat dosing until resolved to \leq grade 2 (fatigue not relieved by rest limiting instrumental activities of daily life), or baseline, then reduce dose by one level alternating between panobinostat and MLN9708, starting with panobinostat.
HEPATIC		
Total Bilirubin	Grade 3-4 ($> 3 \times$ ULN)	Temporarily discontinue panobinostat and MLN9708 dosing until resolved to \leq grade 2, or baseline, then reduce dose by one level alternating between panobinostat and MLN9708, starting with panobinostat.

Worst Toxicity CTCAE Grade* unless otherwise specified (Value)		Dose Modification Guidelines At any time during a cycle of therapy (including intended day of dosing)
AST/SGOT, ALT/SGPT	> 5-10 x ULN	Temporarily discontinue panobinostat and MLN9708 dosing until resolved to \leq grade 1 (or \leq grade 2 if liver infiltration with myeloma is present), or baseline, then: 
 • If resolved within 7 days, then: 
 • restart panobinostat and MLN9708 at unchanged dose levels If resolved in more than 7 days, then reduce dose by one level alternating between panobinostat and MLN9708, starting with panobinostat.
	> 10 x ULN	Temporarily discontinue panobinostat dosing until resolved to \leq grade 1, or baseline, then reduce dose by one level alternating between panobinostat and MLN9708, starting with panobinostat.
Other NON-HEMATOLOGICAL TOXICITIES		
Grade 2 with clinically significant impact on quality of life		Consider holding study drug(s) felt to be responsible and restarting at reduced level and/or with improved supportive measures upon satisfactory improvement.
Grade 3		Hold study drug(s) felt to be responsible and restart at reduced dose level upon resolution to Grade \leq 1 or baseline.
Grade 4		Strongly consider permanently discontinuing study drug(s) felt to be responsible but resuming at reduced dose upon resolution to \leq grade 1 or baseline is allowed if clinical judgment suggests net benefit from continued treatment.

Worst Toxicity CTCAE Grade* unless otherwise specified (Value)	Dose Modification Guidelines At any time during a cycle of therapy (including intended day of dosing)
All dose modifications should be based on the worst preceding toxicity.	
* Common Terminology Criteria for Adverse Events (CTCAE Version 4)	
** It is critical that electrolyte abnormalities be followed closely and corrected prior to dosing	
*** See also concomitant medication Section 7.7	

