7.4 Instructions for Initiation of a New Cycle

A new course of treatment may begin on the scheduled Day 1 of a new cycle (cycle 2 and beyond) if:

- $ANC \geq 1.0 \times 10^9/L$ (G-CSF and GM-CSF are allowed to achieve this threshold)
- Platelets $\geq 50 \times 10^9/L$, without platelet transfusion for $\geq 72h$
- AST and $ALT \leq 3 \times ULN$
- Serum bilirubin $\leq 3 \times ULN$
- Serum potassium $\geq LLN$ and serum magnesium $\geq LLN$ (electrolyte levels may be achieved with repletion or other supportive medications like potassium sparing diuretics)
- $QTcF \leq 480$ msec if ECG obtained (mandatory before cycle 2)
- Any non-hematologic drug-related adverse events that may have occurred have resolved to \leq grade 1 or baseline severity. Physician discretion may be used in initiating the next cycle of treatment if the only toxicities that have not resolved to \leq grade 2 severity are dexamethasone-related toxicities.

If these conditions are not met on Day 1 of a new cycle, the subject will be evaluated at least weekly and a new cycle of treatment will not be initiated until the toxicity has resolved as described above. If a prolonged QTcF prevents re-initiation of therapy for more than 7 days the patient will be taken off study. For phase I patients only: If other criteria to initiate a new cycle are not met by 14 days after the planned start of a new cycle patients also go off study.

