Thrombocytopenia has been reported with MLN9708 and panobinostat. Blood counts should be monitored regularly as outlined in the protocol with additional testing obtained according to standard clinical practice. Thrombocytopenia may be severe but has been manageable with platelet transfusions according to standard clinical practice. MLN9708 administration should be modified as noted as per dose modification recommendations in Table 3-2 and Table 7-4 when thrombocytopenia occurs. Therapy can be reinitiated at a reduced level upon recovery of platelet counts.

Neutropenia

Neutropenia has been reported with MLN9708 and panobinostat. Blood counts should be monitored regularly as outlined in the protocol with additional testing obtained according to standard clinical practice. GM-CSF and G-CSF may be used to shorten neutropenic periods and to maintain dose level of study drugs if neutropenia is the only reason for dose reduction according to table Table 7-4 and at the discretion of the treating physician.

Fluid Deficits

Dehydration should be avoided because MLN9708 and panobinostat may cause vomiting, diarrhea, and dehydration. Two cases of acute renal failure have been reported in patients treated at or above the MTD with IV administration of MLN9708. There has been no treatment-related renal failure reported in patients treated with PO MLN9708. Fluid deficits should be corrected before initiation of study drug and during treatment. Until further information is available, intake of NSAIDs while on this protocol should be avoided.

Hypotension

Symptomatic hypotension and orthostatic hypotension have been reported with MLN9708. Blood pressure should be closely monitored while the patient is on study treatment and fluid deficit should be corrected as needed, especially in the setting of concomitant symptoms such as nausea, vomiting, diarrhea, or anorexia. Patients taking medications and/or diuretics to manage their blood pressure (for either hypo- or hypertension) should be managed according to standard clinical practice, including considerations for dose adjustments of their concomitant medications during the course of the trial.

Posterior Reversible Encephalopathy Syndrome

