7.7.2 Summary of prohibited concomitant medications and supplements

The following contains commonly used medications that should not be used during this study due to either pharmacokinetic interactions or pharmacodynamically based increased risk for adverse events. It is not inclusive. See Sections 19-21 for more information.

- Grapefruit or grapefruit juice and seville (sour) oranges (regular orange juice is allowed)

- Non-steroidal anti-inflammatory agents (NSAIDs) should be avoided if possible due to risk for kidney dysfunction in myeloma but if clinical judgement strongly argues for their use patients can remain on study while receiving NSAIDs
- Other antineoplastic agents
- Other investigational agents
- Aprepitant
- All Class IA antiarrhythmics: quinidine, procainamide, disopyramide, any other class IA antiarrhythmic drug
- All Class III antiarrhythmics: amiodarone, sotalol, bretylium, disopyramide, dofetilide, ibutilide, any other class III antiarrhythmic drug
- Calcium channel blockers: diltiazem, verapamil
- The following Antibiotics: Erythromycin, clarithromycin, telithromycin (azithromycin is allowed), enoxacin, sparfloxacin, ciprofloxacin, voriconazole, ketoconazole, and posaconazole
- Antipsychotics/antidepressants: thioridazine, mesoridazine, chlorpromazine, pimozide, fluvoxamine, nefazodone
- Antimalarials: halofantrine, chloroquine
- Miscellaneous drugs: arsenic trioxide, astemizole, bepridil, domperidone, levomethadyl, methadone, pentamidine, droperidol
- Strong inhibitors of CYP1A2: fluvoxamine, enoxacin, ciprofloxacin
- Strong inhibitors of CYP3A: clarithromycin, telithromycin, itraconazole, voriconazole, ketoconazole, nefazodone, and posaconazole
- Strong CYP3A inducers: rifampin, rifapentine, rifabutin, carbamazepine, phenytoin, and phenobarbital
- The dietary supplements St John's wort and Ginkgo biloba are not permitted.

The following procedures are prohibited during the study:

- Any antineoplastic treatment with activity against MM except for drugs in this treatment regimen.
- Radiation therapy (the requirement for local radiation therapy generally indicates disease progression). Platelet transfusions can be given as clinically indicated but eligibility for starting a new cycle needs to be determined after at least 72 h without platelet transfusion and eligibility for inclusion in this trial needs to be determined after at least 7 days without platelet transfusion. Adjuvant hormone therapy for breast or prostate cancer.

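### Restart within a cycle after grade 4 thrombocytopenia accepts a transfused platelet count that Section 7.4 would reject for a new cycle

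*Combined protocol and SAP*

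**What the plan says.** Table 7-4 (Section 7.5.3) covers restarting treatment as well as delays and reductions, and it applies at any point in a cycle, including a planned dosing day. For grade 4 thrombocytopenia (below 25 x 10^9/L) it reads "Temporarily discontinue panobinostat and MLN9708 dosing until platelets have increased to" at least 50 x 10^9/L, "then reduce dose of one of these drugs by one level per cycle starting with panobinostat until panobinostat is at 10mg". It says nothing about platelet transfusion.

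Five other places bear on the same decision:

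- **Section 7.4** (Day 1 of cycle 2 and later) requires platelets of at least 50 x 10^9/L "without platelet transfusion for" at least 72 h. For neutrophils the same list takes the opposite line: "G-CSF and GM-CSF are allowed to achieve this threshold".
- **Section 7.7.2** allows transfusion as clinically indicated, but "eligibility for starting a new cycle needs to be determined after at least 72 h without platelet transfusion". It also sets 7 days for trial entry. It does not mention restart within a cycle.
- **Section 7.6** describes platelet transfusion as the way severe thrombocytopenia is managed, and then says: "Therapy can be reinitiated at a reduced level upon recovery of platelet counts". Recovery is not defined.
- **Section 7.7.1** also permits platelet transfusion as clinically indicated.
- **Section 5.4** makes a platelet transfusion in cycle 1 a dose-limiting toxicity, but lets the patient stay on study and sets no condition for re-dosing.

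**The concern.** The protocol checks the platelet count at three points. Entry requires 7 days without transfusion, a new cycle requires 72 h, and restart within a cycle requires no interval. The third check follows the most severe platelet toxicity in the table, in the patients most likely to have been transfused.

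A transfused count can reach 50 x 10^9/L while the patient's own production has not recovered. At a first event from full dose, panobinostat would restart at 15 mg instead of 20 mg (Table 7-2), and ixazomib would continue at its current dose. What is at stake is patient safety at one dosing decision. No endpoint, analysis set or estimate depends on it.

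**Working it through.** **Rules side by side**

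| Decision | Platelet threshold | Transfusion-free interval |
|---|---|---|
| Trial entry (6.1.2, 7.7.2) | 70 x 10^9/L | 7 days |
| New cycle (7.4, 7.7.2) | 50 x 10^9/L | 72 h |
| Restart within a cycle after grade 4 (Table 7-4) | 50 x 10^9/L | none stated |

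No other section applies an interval to the third row.

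**When the gap could matter.** Four things must coincide: grade 4 thrombocytopenia, a transfusion, a later count of at least 50 x 10^9/L, and a dose due within 72 h of the transfusion. The calendar part can be counted.

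Inputs: after Day 1, panobinostat falls on days 3, 5, 15, 17 and 19, and ixazomib on days 8 and 15 (Section 5.3). Weekly counts are taken as days 8, 15 and 22, each with a window of +/- 3 days (Table 8-1 note).

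Assumptions: grade 4 is found on a scheduled count; the transfusion is given that day (t) and that day's dose is held; restart needs a later count (q > t); the next dose is the first dosing day d >= q; held doses are not made up. The gap is (d - t) x 24 h.

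1. *Exact weekly days.* For t = 8, q = 15, the dose is on day 15 and the gap is 7 x 24 = 168 h. For t = 15, q = 22, no dose remains in the cycle. Result: 0 of 2 pairs are inside 72 h.
2. *First to second window* (t = 5 to 11, q = 12 to 18; 7 x 7 = 49 pairs). The smallest gap is day 11 to day 15, 4 x 24 = 96 h. Result: 0 of 49.
3. *Second to third window* (t = 12 to 18, q = 19 to 25; 49 pairs). Only q = 19 leaves a dose, panobinostat on day 19. For t = 18 the gap is 24 h, for t = 17 it is 48 h, and for t = 16 it is 72 h, which passes. Result: 2 of 49.
4. *Total with windows:* 2 of 98. A transfusion on days 19 to 25 leads to Day 1 of the next cycle, where Section 7.4 applies.
5. *With an unscheduled count after the transfusion* (Section 9.1.4 permits these). Transfusion days with a later dose inside 72 h are 6 and 7 (dose day 8), 13 and 14 (day 15), 15 and 16 (day 17), and 17 and 18 (day 19). Result: 8 of the 14 days from 5 to 18.

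These are counts of calendar possibilities, not probabilities. Weekly counts are scheduled only through cycle 2 (Table 8-1, footnote 10). From cycle 3, counts within a cycle are taken as clinically indicated, and phase II treatment continues until a discontinuation criterion is met (Section 5.2).

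**How often the trigger occurs.** The Phase II extension text in Section 2 reports one grade 3 and no grade 4 thrombocytopenia among 11 phase I patients. With 0 of 11, the one-sided 95% upper bound is 1 - 0.05^(1/11) = about 24%, so phase I does not show that grade 4 is rare. No rate is given for the later steps.

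**The case against.** The strongest reply is that restart within a cycle may be meant to be easier. After grade 4 neutropenia, dosing restarts at an ANC of 0.5 x 10^9/L, against 1.0 x 10^9/L for a new cycle. Transaminases must be no more than 3 x ULN for a new cycle, while a hold during a cycle begins only above 5 x ULN. Table 7-4 also has no grade 3 thrombocytopenia row, so a patient at 30 x 10^9/L who never reached grade 4 continues both drugs. The amendment log shows that the sponsor considered transfusion intervals when the 72 h wording entered Sections 7.4 and 7.7.2, so the omission could be deliberate. Clinicians may also reduce by more than one level (Section 7.5.1), interrupt ixazomib as needed (Section 7.1.2), or read recovery in Section 7.6 as unsupported recovery. Finally, the documents give no specific basis for 72 h within a cycle.

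Part of this stands. The missing grade 3 row means the added risk falls mainly on patients whose own count is still below 25 x 10^9/L. Discretion makes a harmful restart less likely, and the log is compatible with intent.

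It does not remove the point. For neutrophils the threshold itself differs between the two rules. For platelets it is identical, and only the condition that makes the number interpretable is absent. The liver comparison sets a trigger for holding against a criterion for starting, so it is not like for like. Once grade 4 has occurred, the protocol itself demands 50 x 10^9/L before re-dosing, and a transfusion can meet that demand without recovery. Nothing in the documents says this is intended.

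**Conclusion.** The concern holds. Followed literally, Table 7-4 lets panobinostat and ixazomib restart within a cycle on a transfused count of at least 50 x 10^9/L, which Section 7.4 would not accept for a new cycle within 72 h of the transfusion.

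The practical size is small and not estimable from the documents. Under the calendar assumptions above, scheduled counts expose at most a single panobinostat dose on day 19. The ixazomib dose on day 8, both drugs on day 15 and panobinostat on day 17 are reached only through unscheduled counts. Day 1 of cycle 2 and later is not affected. Confidence is high in the reading of the text. Whether the omission was deliberate, and how often it would matter, remain unknown. This is an optional, inexpensive safety improvement.

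**What to change.** In the grade 4 thrombocytopenia row of Table 7-4, add after the 50 x 10^9/L threshold that no platelet transfusion may have been given for at least 72 h, matching Section 7.4. In Section 7.6, define platelet recovery by reference to that row. If the looser rule is intended, say so in the row.

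The change is one phrase and one cross-reference. Section 11 requires a written amendment reviewed by both drug suppliers, so it can go with the next planned amendment. The clinical cost is that an affected patient may have a dosing day delayed or omitted, or more than one if transfusions are repeated.

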Phase II extension: Patients in phase I (median age 65, range 50-73, median previous regimens 5, range 2-10) tolerated treatment without DLT and without non-hematologic severe (grade 3 or higher) adverse event according to CTCAE vs.4.03. Three patients developed grade 3 hematologic toxicities (2 neutropenia, 1 thrombocytopenia). Worst diarrhea was grade 1 (n=6), worst nausea grade 2 (n=1) and 4 additional patients developed transient grade 1 nausea. Other possibly panobinostat or ixazomib related grade 1/2 adverse events included thrombocytopenia (n=5), neutropenia (n=3), fatigue (n=2), anemia (n=2), anorexia (n=1) and arthralgia (n=1).

Median QTcF before treatment start was 405 msec (range 378-430) and increased on average by 4.3% (maximally by 13%). One patient developed transient grade 1 QTcF prolongation to 552 msec. No other cardiac adverse events were observed. Of the 11 patients in phase I, one reached PR, two reached MR, and one had stable disease for 6 months. All patients entered the study with disease refractory to their last regimen, and in two of the responding patients (1PR, 1MR) this included a proteasome inhibitor an IMiD, and a glucocorticosteroid (carfilzomib, pomalidomide, dexamethasone in the MR patient, bortezomib, dexamethasone, lenalidomide in the MR patient). Overall, we are encouraged by activity in extensively pretreated patients and by excellent tolerance of this regimen so far. In phase II we aim to extend the study cohort by an additional 20 patients who will be treated until progression or other reasons for discontinuation arise (7.6.1) to strengthen the safety analysis and obtain a more reliable estimate of activity.

3 Study objectives

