7.1.2 MLN9708 (Ixazomib)

All protocol-specific criteria for administration of study drug must be met and documented before drug administration. Study drug will be administered only to eligible patients under the supervision of the investigator or identified sub investigator(s). Patients should be monitored for toxicity, as necessary, and doses of MLN9708 should be modified as needed to accommodate patient tolerance to treatment; this may include symptomatic treatment, dose interruptions, and adjustments of MLN9708 dose (see under 7.5).

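### Table 7-4 holds both panobinostat and MLN9708 at AST/ALT above 5 to 10 × ULN but panobinostat alone above 10 × ULN, leaving day 8 and day 15 MLN9708 doses without a required hold at the higher level

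*Combined protocol and SAP*

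**What the plan says.** The hepatic part of Table 7-4 in Section 7.5.3 has two AST/ALT rows.

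- **Above 5 and up to 10 × ULN:** "Temporarily discontinue panobinostat and MLN9708 dosing until resolved to" grade 1 or lower (grade 2 or lower if myeloma infiltrates the liver) or baseline. If recovery takes 7 days or less, both drugs restart at unchanged doses. If it takes longer, doses are reduced.
- **Above 10 × ULN:** "Temporarily discontinue panobinostat dosing until resolved to" grade 1 or lower, or baseline; "then reduce dose by one level alternating between panobinostat and MLN9708, starting with panobinostat".

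A note under the table says "All dose modifications should be based on the worst preceding toxicity". The column heading applies the rules at any time in a cycle, including an intended dosing day. MLN9708 is given on days 1, 8 and 15 of 28, at 4 mg in phase II (Section 5.3).

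**The concern.** A dose-hold rule should be at least as protective at a higher level of liver injury as at a lower one. Here the drugs held go from two to one as AST/ALT crosses 10 × ULN. Followed literally, the table lets a patient at 12 × ULN take MLN9708 on day 8 or 15, when the same patient at 7 × ULN would have had it stopped.

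The row's own reduction step treats MLN9708 as a possible contributor, since reductions alternate between the two drugs. But the sequence starts with panobinostat. At a first event above 10 × ULN, the row therefore neither holds nor reduces MLN9708. Section 1.3.7 describes metabolism as MLN9708's apparent main route of elimination and gives a terminal half-life of about 5 to 7 days. It is my inference that dosing through severe liver injury is undesirable; the documents give no exposure data in hepatic impairment.

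What is at stake is patient safety, not inference. Section 13.1.1.2 reports toxicity descriptively, and no analysis of dose holds is planned.

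**Working it through.** The plan has no figure of its own to reproduce here. The check is a comparison of text, followed by simple bounds on size.

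**Step 1. Is the narrower hold a pattern in the table?** Ten rows of Table 7-4 order a hold followed by reductions shared between the two drugs.

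| Row | Drugs held |
|---|---|
| Thrombocytopenia, grade 4 | both |
| Neutropenia, grade 4 | both |
| Febrile neutropenia | both |
| Diarrhea, grade 2 | both |
| Diarrhea, grade 3 | both |
| Nausea/vomiting, uncontrolled grade 3 or worse | both |
| Fatigue, grade 3 | panobinostat only |
| Bilirubin, grade 3–4 | both |
| AST/ALT above 5 to 10 × ULN | both |
| AST/ALT above 10 × ULN | panobinostat only |

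Eight of ten hold both. The fatigue row has no lower band, so nothing is reversed there. AST/ALT is the only toxicity whose hold narrows with severity. In other respects the above-10 × ULN row is the stricter one: reduction is mandatory whatever the recovery time, and there is no allowance for liver infiltration. That pattern fits an omitted 'and MLN9708' better than a deliberate relaxation.

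**Step 2. Does another rule stop MLN9708 on day 8 or 15?**

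- Section 7.4 requires AST and ALT at or below 3 × ULN, and "a new cycle of treatment will not be initiated until the toxicity has resolved as described above". This applies on day 1 of cycle 2 and later, not on day 8 or 15.
- Section 7.5.1: "Clinical judgment may be used when deciding which drug to hold or modify in scenarios that are not covered below". AST/ALT above 10 × ULN is covered. The separate permission there to hold a drug concerns events judged unrelated to study drug, whereas Table 7-4 governs drug-related toxicity.
- The general grade 3 and grade 4 rows of Table 7-4 are for other non-hematologic toxicities.
- Section 7.1.2: "doses of MLN9708 should be modified as needed to accommodate patient tolerance to treatment". This is a general duty that refers back to Section 7.5.
- Section 9.1.4 requires laboratory review before either drug is given, but the reviewer is then sent to this same row.
- Section 7.6.1 permits withdrawal for adverse events or abnormal laboratory values; it does not order it.
- Section 5.4 lets a patient with a dose-limiting toxicity stay on study.

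None requires a within-cycle MLN9708 hold.

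**Step 3. Doses exposed per event.** Section 7.4 blocks the next day 1, so at most days 8 and 15 are uncovered: 2 doses × 4 mg = 8 mg.

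**Step 4. How often might it arise?** Section 2 (Phase II extension) states that the 11 phase I patients were treated "without non-hematologic severe (grade 3 or higher) adverse event according to CTCAE vs.4.03". Assume that AST/ALT above 10 × ULN is at least grade 3, so the count is 0 of 11.

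- Exact two-sided 95% upper limit: 1 − 0.025^(1/11) = 0.285. Times 20 phase II patients: 5.7.
- Exact one-sided 95% upper limit: 1 − 0.05^(1/11) = 0.238. Times 20: 4.8.
- Chance of at least one event in 20 patients, 1 − (1 − p)^20, at assumed rates p: 1% gives 0.182, 2% gives 0.332, 5% gives 0.642.

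**The case against.** **An active hold continues.** A patient already held at 7 × ULN has both drugs off until recovery, and a rise to 12 × ULN does not meet that release condition. Reading the worst-toxicity note as lifting the MLN9708 hold is possible but strained. This has force, and I would not rest the point on that transition. The gap is clear for a patient first found above 10 × ULN, who never entered the lower row.

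**Silence is not an instruction to dose.** The table is headed as guidelines. Pre-dose laboratory review, the general duty in Section 7.1.2, the option in Section 7.5.1 to reduce by more than one level and the right to withdraw a patient all let a physician stop MLN9708. Many would. This lowers the practical risk, but the table requires a two-drug hold at the lower level and does not at the higher one.

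**The size figures are loose.** This is fair. The 28.5% limit comes from the absence of any grade 3 or higher non-hematologic event, so it is a ceiling and not an estimate for AST/ALT. The 1%, 2% and 5% rates are not from the documents. The chances count every event above 10 × ULN, but the gap matters only if the event is drug-related, is detected with a day 8 or 15 dose still due, and is not already under a hold. Two exposed doses require detection by day 8, from a cycle-start value of at most 2.5 × ULN (entry) or 3 × ULN (later cycles).

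**The documents do not tie liver injury to MLN9708.** The risk list in Section 1.3.12 names no hepatic toxicity, and Section 1.2.3 describes liver-test changes with panobinostat. A panobinostat focus could be defended, but it does not explain why the milder AST/ALT row and the bilirubin row hold both drugs.

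**Conclusion.** The concern holds. Table 7-4 is less protective above 10 × ULN than at 5 to 10 × ULN, and no other provision requires MLN9708 to be held on day 8 or 15. The exposure is small: up to 2 doses (8 mg) per event.

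The event is probably uncommon. Phase I gives 0 of 11, compatible with a rate of up to 28.5%. That bound assumes the above-10 × ULN range falls in grade 3 or higher, and that phase II risk resembles phase I, which also treated patients at 3 mg and was planned for six cycles. At assumed rates of 1% to 5%, the chance of at least one such event among 20 phase II patients is 18% to 64%; these are upper figures for the gap itself, for the reasons given under the objection.

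No planned analysis is biased. The point should still be fixed, because safety should not depend on physicians going beyond the written rule. Phase II treatment has no fixed cycle limit (Section 5.2), and weekly chemistry is scheduled only through cycle 2 (Section 8, footnote 10).

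**What to change.** In the AST/ALT above-10 × ULN cell of Table 7-4, add 'and MLN9708' so that the instruction opens with "Temporarily discontinue panobinostat and MLN9708 dosing until resolved to" grade 1 or lower, or baseline. Leave the mandatory alternating reduction in that row as it is.

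The cost is two words in one table cell, made by amendment. Assessments, sample size and analysis do not change. The clinical price is an occasional missed MLN9708 dose, which the plan already accepts at half that AST/ALT level.
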